The data of study drugs on pregnant women is limited or not available. There is no suspicion of human teratogenicity based on class effects or genotoxic potential. Relevant non clinical reproductive toxicity studies for human pregnancy do not indicate a strong suspicion of human teratogenicity/fetotoxicity. Data from clinical pharmacokinetic interaction studies of study drug have demonstrated that there is no reduction in the clinical efficacy of hormonal contraception or that the effect on hormonal contraception is insignificant. Please refer to the latest version of the investigator's brochure for additional information.

b) Contraception Requirements for Female Subjects of Childbearing Potential

The inclusion of female subjects of childbearing potential requires the use of highly effective contraceptive measures. They must also not rely on hormone-containing contraceptives as a form of birth control during the study. They must have a negative serum pregnancy test at Screening prior to study enrollment. A serum pregnancy test will be performed at all study visits and the end of relevant system exposure. In the event of a delayed menstrual period (over one month between menstruations), a serum pregnancy test must be performed to rule out pregnancy. This is even true for women of childbearing potential with infrequent or irregular periods. Female subjects must agree to one of the following from Screening until 30 days following the end of relevant systemic exposure.

- Complete abstinence from intercourse of reproductive potential. Abstinence is an acceptable method of contraception only when it is in line with the subject's preferred and usual lifestyle.

Or

- Consistent and correct use of 1 of the following methods of birth control listed below:
 - Intrauterine device (IUD) with a failure rate of < 1% per year
 - Tubal sterilization
 - Essure micro-insert system (provided confirmation of success 3 months after procedure)
 - Vasectomy in the male partner (provided that the partner is the sole sexual partner and had confirmation of surgical success 3 months after procedure)

Or

- Consistent and correct use of one hormonal method and one barrier method:
 - Barrier methods
 - Diaphragm with spermicide
 - Cervical cap with spermicide
 - Male condom (with or without spermicide)
 - Hormonal methods (the hormonal contraceptive should contain at least 30 mcg of ethinyl estradiol)
 - Intrauterine hormone-releasing system (IUS) with a failure rate of < 1% per year
 - Oral contraceptives (either combined or progesterone only)
 - Injectable progesterone
 - Implants of levonorgestrel
 - Transdermal contraceptive patch
 - Contraceptive vaginal ring

Female subjects must also refrain from egg donation and in vitro fertilization during treatment and until at least 30 days after the end of relevant systemic exposure.

3) Contraception Requirements for Male Subjects

During the study, male subjects with female partners of childbearing potential should use condoms when engaging in intercourse of reproductive potential.

4) Unacceptable Birth Control Methods

Birth control methods that are unacceptable include periodic abstinence (e.g., calendar, ovulation, symptothermal, post-ovulation methods), withdrawal (coitus interruptus), spermicides only, and lactational amenorrhea method (LAM). Female condom and male condom should not be used together.

5) Procedures to be Followed in the Event of Pregnancy

Subjects will be instructed to notify the investigator if they become pregnant at any time during the study, or if they become pregnant within 30days of last study drug dose. Subjects who become pregnant or who suspect that they are pregnant during the study must report the information to the investigator and discontinue study drug immediately. Subjects whose partner has become pregnant or suspects she is pregnant during the study must report the information to the investigator. Instructions for reporting pregnancy, partner pregnancy, and pregnancy outcome are outlined in Section [7.5.2.1](#).

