- 12) Serum amylase $\leq 5 \times$ ULN (subjects with serum amylase $> 5 \times$ ULN will remain eligible if serum lipase is $\leq 5 \times$ ULN)
- 13) A female subject is eligible to enter the study if it is confirmed that she is:
 - a) Not pregnant confirmed by a negative serum pregnancy test (unless permanently sterile or greater than two years post-menopausal)
 - b) Of non-child bearing potential (i.e. women who have had a hysterectomy, have had both ovaries removed or medically documented ovarian failure, or are postmenopausal women > 54 years of age with cessation (for ≥ 12 months) of previously occurring menses
Female subjects who have stopped menstruating for ≥ 12 months but do not have documentation of ovarian hormonal failure must have a serum follicle stimulating hormone (FSH) level at screening within the post-menopausal range based on the Central Laboratory Reference range.
 - c) Of childbearing potential and agrees to utilize the protocol specified method of contraception or be non-heterosexually active or practice abstinence from screening throughout the duration of the study treatment and for 30 days following study drug discontinuation (as defined in [Appendix 7](#))
 - d) Female subjects who utilize hormonal contraception as one of the birth control methods must have used the same method for at least three months prior to the study dosing.
- 14) Male subjects must agree to use protocol specified method(s) of contraception from screening throughout the duration of study treatment and for 30 days following discontinuation of study drugs ([Appendix 7](#)).
- 15) Male subjects must agree to refrain from sperm donation from first dose until at least 30 days after the last study drug dose.
- 16) Lactating females must agree to discontinue nursing before the study drug is administered.

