5.4. Prior and Concomitant Medications

- For subjects receiving hormonal contraceptives, investigators and/or the subject's healthcare providers should consider additional methods of contraception, as concentrations of ethinyl estradiol may decrease and progestin level may increase on co-administration with study drug.
- The use of medications for the treatment of HIV, other than study drug, is prohibited.
- For subjects receiving concomitant medications that are highly dependent on CYP3A for clearance and for which elevated plasma concentrations are associated with serious adverse events, investigators and/or the subject's healthcare providers should consider alternative concomitant medications.
- During the study, subjects may not receive any of the following concomitant medications:
 - Competitors of renal excretion (e.g., probenecid; high-dose non-steroidal anti-inflammatory drugs)
 - Known nephrotoxic drugs (e.g., aminoglycosides, amphotericin B, vancomycin, cidofovir, foscarnet, cisplatin and pentamidine)
- Medications listed in the following tables and use of herbal/natural supplements are excluded or should be used with caution while subjects are participating in the study. Any concomitant medication requiring adjustment or discontinuation due to renal impairment or a change in renal function on study should be managed per that drug's prescribing information.

Table 5-1. Prior and Concomitant Medications (E/C/F/TAF)

Drug Class	Agents Disallowed	Use Discouraged and To Be Used With Caution
Acid Reducing Agents Antacids		Concentration of study drug may decrease with antacids. Subjects may not take antacids (eg, Tums, Mylanta); the ulcer medication sucralfate (Carafate); or vitamin or mineral supplements that contain calcium, iron or zinc for a minimum of 2 hours before and 2 hours after any dose of study drug.
Alpha Adrenergic Receptor Antagonists	Alfuzosin	
Analgesics		Tramadol, Propoxyphene: Concentrations may increase with study drug(s); clinical monitoring is recommended.
Antiarrhythmics		Amiodarone, Flecainide, Quinidine, Propafenone, Systemic Lidocaine, Mexiletine, Disopyramide: Concentrations may increase with study drug(s) resulting in a potential for cardiac arrhythmias; clinical and ECG monitoring is recommended.
Calcium Channel Blockers	Bepridil	Felodipine, Nifedipine, Nicardipine, Verapamil, Diltiazem, Amlodipine: Concentrations may increase with study drug(s). Clinical and ECG monitoring of subjects is recommended

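### Appendix 7 tells women of childbearing potential not to rely on hormonal contraception, then accepts it with a barrier, and attaches an ethinyl estradiol minimum that some of its listed methods cannot meet

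*Protocol*

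**What the plan says.** Protocol Section 4.2, criterion 13c, ties a woman's eligibility to the contraceptive method defined in Appendix 7, from screening through treatment and for 30 days afterwards. Criterion 13d adds a condition for hormonal users: "Female subjects who utilize hormonal contraception as one of the birth control methods must have used the same method for at least three months" before dosing.

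Appendix 7, item 2b, gives the rule itself. Its opening paragraph says of women of childbearing potential: "They must also not rely on hormone-containing contraceptives as a form of birth control during the study". It then offers three routes: abstinence; one method from a list of devices and sterilization procedures; or "Consistent and correct use of one hormonal method and one barrier method". The list for the third route opens with "Hormonal methods (the hormonal contraceptive should contain at least 30 mcg of ethinyl estradiol". Six entries follow: a hormone-releasing intrauterine system, oral contraceptives, injectables, implants, a patch and a vaginal ring. The oral entry reads "Oral contraceptives (either combined or progesterone only", the injectable entry reads "Injectable progesterone", and the implants are named as levonorgestrel.

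Section 5.4 advises prescribers to consider extra contraception for hormonal users because "concentrations of ethinyl estradiol may decrease and progestin level may increase on co-administration with study drug". Table 5-1 has a row for hormonal contraceptives.

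On menopause, criterion 13b sets the age limit at over 54, while Appendix 7, item 1a, sets it at 54 or over. Both use 12 months without menses. Criterion 13a waives the pregnancy test for women who are permanently sterile or more than two years post-menopausal.

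**The concern.** This is a rule that sites must apply, and women on treatment must follow it until at least 30 days after they stop. A woman using a hormonal method with a condom can find her method accepted by one sentence of Appendix 7, barred by another, and in some cases short of the ethinyl estradiol condition as well. Two sites could give her different advice, each with support in the text.

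Pregnancy is the outcome that the rule exists to prevent, and item 5 of Appendix 7 requires study drug to be stopped at once if it occurs. The rule also affects reporting. SAP Section 4.3 lists every enrolled subject who violated an inclusion or exclusion criterion, and whether a hormonal user meets 13c depends on which sentence is applied.

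**Working it through.** No arithmetic applies, because the plan gives no figure to reproduce. The check sets the passages side by side.

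**Conflict 1: the must-not-rely sentence against the rest.** The sentence carries no qualifier such as *solely*. Against it stand the third route in the same item, criterion 13d, the Section 5.4 advice and the hormonal row in Table 5-1. Each of these would have no purpose if hormonal contraception were barred.

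**Conflict 2: the ethinyl estradiol condition against its own list.** The condition stands in the heading over all six entries. The table below applies both rules to each entry used with a barrier, taking product content only from the names in the list. The oral entry is split because it names two types.

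| Entry | Method list | Ethinyl estradiol condition | Must-not-rely sentence, read literally |
|---|---|---|---|
| Intrauterine system | accepted | content not stated | excluded |
| Oral, combined | accepted | depends on dose | excluded |
| Oral, progesterone-only | accepted | cannot be met | excluded |
| Injectable progesterone | accepted | cannot be met | excluded |
| Levonorgestrel implant | accepted | cannot be met | excluded |
| Patch | accepted | content not stated | excluded |
| Vaginal ring | accepted | content not stated | excluded |

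Two of the six entries (injectable and implant) fail the condition outright, and one (oral) fails in part. For the other three the documents do not give the content.

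**Minor mismatch: menopause.** A woman aged exactly 54 with 12 months without menses is postmenopausal by age under Appendix 7 but not under 13b. A 56-year-old who is 18 months past menopause is of non-childbearing potential under 13b. Under 13a she still needs a negative pregnancy test, yet Section 6.2.1 schedules that test only for women of childbearing potential.

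**The case against.** The best defense is to read the passages together. Appendix 7 never accepts a hormonal method without a barrier, 13d speaks of hormones as one among several methods, and Section 5.4 expects hormonal users in the study. On that view, not relying on hormones means not relying on them alone. Likewise, the ethinyl estradiol condition uses *should*, not *must*, and can be taken to cover only products that contain it. Both readings are workable, but neither is written down. The first needs a word that the sentence lacks. The second needs a limit that the heading does not state.

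Several stronger readings are tempting and do not hold:

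- **Section 5.4 contradicts Appendix 7 on drug interaction.** Section 5.4 concerns plasma concentrations. Appendix 7, item 2a, concerns clinical efficacy. Concentrations can change without a loss of efficacy, so both can be true.
- **The intrauterine system also fails the ethinyl estradiol condition.** The documents do not give its content.
- **Sites would make opposite enrollment decisions.** This is largely past. Protocol Section 1.2.5 already reports Week 48 results on 55 subjects, and the SAP's disposition table shows 55 enrolled and treated.
- **Pregnancy would remove women from the analysis.** The SAP's full and safety analysis sets (Sections 3.1.3 to 3.1.6) need only one dose, and the snapshot algorithm (Section 7.2.1) has a category for those who stop drug. Protocol Section 6.5.2 asks women who stop E/C/F/TAF to keep attending through Week 96. In the extension, Section 6.5.1 ends scheduled visits after early stopping, so later observations would be lost, but not membership of the sets. Protocol Section 8.2.1.1 does exclude major protocol violations from the full analysis set, but the SAP definition has no such exclusion.

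The practical risk is also tempered. Section 1.2.5 reports no pregnancy up to the data cut, and Appendices 2 and 3 schedule a serum pregnancy test at every visit. The menopause differences are small: the age gap affects only women of exactly 54, and both places offer a route by follicle-stimulating hormone level.

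**Conclusion.** The two conflicts in Appendix 7, item 2b, stand on the text. The first has a charitable reading that the wording does not express. The second has no consistent literal reading while the condition heads the whole list. The menopause wording is a minor inconsistency.

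The consequence is for subject safety, for uniform application of the rule during continued treatment and the B/F/TAF extension, and for who appears in the SAP's listing of eligibility violations. The primary endpoint, the sample size and the SAP analysis sets are unaffected. The number of women of childbearing potential using a hormonal method is not given, so the reach cannot be quantified. The conclusion assumes only that progesterone-only products, injectable progesterone and levonorgestrel implants contain what their names say. The point merits correction but is not critical to the trial's conclusions.

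**What to change.** The sponsor should:

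1. Reconcile the must-not-rely sentence in Appendix 7, item 2b, with the hormonal-plus-barrier route, criterion 13d and Section 5.4.
2. Reconcile the ethinyl estradiol condition with the methods listed under it.
3. Use one postmenopausal definition in criterion 13 and Appendix 7, and align the pregnancy-test waiver in 13a with the testing schedule in Section 6.2.1.
4. Notify sites, and apply the reconciled text when flagging violations for the SAP Section 4.3 listing.

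Which version stands is a clinical decision for the sponsor, and none is proposed here. The cost is wording changes in Appendix 7 and criterion 13, possibly in Sections 5.4 and 6.2.1, and a letter to sites. No data collection or analysis changes. The site letter is useful for as long as any woman is on study drug or within the follow-up period that the contraception rule covers.

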Appendix 8. Definitions of HIV-1 Related Disease (CDC Guidelines) {Selik 2014}

- Bacterial infections, multiple or recurrent*
- Candidiasis of bronchi, trachea, or lungs
- Candidiasis of esophagus
- Cervical cancer, invasive†
- Coccidioidomycosis, disseminated or extrapulmonary
- Cryptococcosis, extrapulmonary
- Cryptosporidiosis, chronic intestinal (> 1 month's duration)
- Cytomegalovirus disease (other than liver, spleen, or nodes), onset at age > 1 month
- Cytomegalovirus retinitis (with loss of vision)
- Encephalopathy attributed to HIV§
- Herpes simplex: chronic ulcers (> 1 month's duration) or bronchitis, pneumonitis, or esophagitis (onset at age > 1 month)
- Histoplasmosis, disseminated or extrapulmonary
- Isosporiasis, chronic intestinal (> 1 month's duration)
- Kaposi sarcoma
- Lymphoma, Burkitt (or equivalent term)
- Lymphoma, immunoblastic (or equivalent term)
- Lymphoma, primary, of brain
- *Mycobacterium avium* complex or *Mycobacterium kansasii*, disseminated or extrapulmonary
- *Mycobacterium tuberculosis* of any site, pulmonary†, disseminated, or extrapulmonary
- Mycobacterium, other species or unidentified species, disseminated or extrapulmonary
- *Pneumocystis jirovecii* (previously known as "*Pneumocystis carinii*") pneumonia
- Pneumonia, recurrent†

- Progressive multifocal leukoencephalopathy
- *Salmonella* septicemia, recurrent
- Toxoplasmosis of brain, onset at age > 1 month
- Wasting syndrome attributed to HIV[§]

* Only among children aged < 6 years

† Only among adults, adolescents, and children aged \geq 6 years

§ Suggested diagnostic criteria for these illnesses, which might be particularly important for HIV encephalopathy and HIV wasting syndrome, are described in the following references {[Centers for Disease Control and Prevention 1992](#), [Centers for Disease Control and Prevention 1994](#)}.

Table 3-3.	Analysis Windows for prothrombin time and INR (E/C/F/TAF Phase).....	18
Table 3-4.	Analysis Windows for SF-36 and HIV-TSQc (E/C/F/TAF Phase)	18
Table 3-5.	Analysis Windows for HIV-TSQs (E/C/F/TAF Phase).....	18
Table 3-6.	Analysis Windows for Safety ECG (E/C/F/TAF Phase)	19
Table 3-7.	Analysis Windows for HIV-1 RNA, CD4 Cell Count, CD4%, Hematology ^a , Chemistry ^b , eGFR _{CG} , Vital Signs, and Weight (B/F/TAF OL Extension Phase)	19
Table 3-8.	Analysis Windows for Fasting Glucose and Lipid Panel (B/F/TAF OL Extension Phase)	19
Table 3-9.	Analysis Windows for SF-36 and HIV-TSQ (B/F/TAF OL Extension Phase)	20
Table 3-10.	Analysis Windows for Safety ECG (B/F/TAF OL Extension Phase)	20

LIST OF ABBREVIATIONS

ABC	abacavir
AE	adverse event
AIDS	acquired immunodeficiency syndrome
ALP	alkaline phosphatase
ALT	alanine aminotransferase
ARV	antiretroviral
AST	aspartate aminotransferase
B/F/TAF	bictegravir 50 mg/emtricitabine 200 mg/tenofovir alafenamide 25 mg fixed-dose combination, Biktarvy®
BMI	body mass index
BLQ	below the limit of quantitation
CDER	Center for Drug Evaluation and Research
CG	Cockcroft-Gault
CI	confidence interval
COBI	cobicistat (Tybost®)
CPK	creatinine phosphokinase
CRF	case report form
CV	coefficient of variation
E/C/F/TAF	single-tablet regimen of elvitegravir (EVG) 150 mg/ cobicistat (COBI) 150 mg / emtricitabine (FTC) 200 mg/ tenofovir alafenamide (TAF) 10mg; coformulated; Genvoya®
ECG	electrocardiogram
eCRF	electronic case report form
eGFR	estimated glomerular filtration rate
eGFR _{CG}	estimated glomerular filtration rate calculated using the Cockcroft-Gault formula
ESDD	early study drug discontinuation
ESRD	end stage renal disease
EVG	elvitegravir
FAS	Full Analysis Set
FDA	Food and Drug Administration
FDC	fixed-dose combination
FTC	emtricitabine (Emtriva®)
GFR	glomerular filtration rate
GSI	Gilead Sciences, Inc.
HD	hemodialysis
HDL	high-density lipoprotein
HIV-1	human immunodeficiency virus (type 1)
HLGT	high level group terms
HLT	high level term

IDMC	independent data monitoring committee
INR	international normalized ratio of prothrombin time
LOCF	last observation carried forward
LDL	low-density lipoprotein
LLT	lowest level term
LLOQ	lower limit of quantitation
MedDRA	Medical Dictionary for Regulatory Activities
OL	open label
PBMC	peripheral blood mononuclear cell
PK	pharmacokinetic
PT	preferred term
PTH	parathyroid hormone
Q	quartile
Q1	first quartile
Q3	third quartile
RNA	ribonucleic acid
SAE	serious adverse event
SAP	statistical analysis plan
Scr	serum creatinine concentration
SD	standard deviation
SMQ	Standardised MedDRA Query
SOC	system organ class
STB	elvitegravir/cobicistat/emtricitabine/tenofovir disoproxil fumarate, coformulated; Stribild®
STR	single-tablet regimen
TAF	tenofovir alafenamide
TDF	tenofovir disoproxil fumarate (Viread®)
TEAE	Treatment-emergent adverse event
TFL	tables, figures, and listings
TFV	tenofovir
ULN	upper limit of normal
VAS	visual analogue scale
WHO	World Health Organization

1. INTRODUCTION

This statistical analysis plan (SAP) describes the statistical analysis methods and data presentations to be used in tables, figures, and listings (TFLs) of the final analysis for Study GS-US-292-1825, which will be performed when all subjects have completed the study or prematurely discontinued from the study. This SAP is based on the study Protocol Amendment 2.1, dated 01 May 2018, and electronic case report form (eCRF). The SAP will be finalized before database finalization. Any changes made to the analyses after the finalization of the SAP will be documented in the final clinical study report. Analyses that were performed as part of interim clinical study reports will not be repeated for the final analysis unless otherwise specified.

1.1. Study Objectives

The primary objective of this study is as follows:

- To evaluate the safety and tolerability of elvitegravir/cobicistat/emtricitabine/tenofovir alafenamide (EVG/COBI/FTC/TAF; E/C/F/TAF) fixed-dose combination (FDC) in HIV-1 infected adults with end stage renal disease (ESRD) on chronic hemodialysis (HD) at Week 48

The secondary objectives of this study are as follows:

- To evaluate the safety and tolerability of the E/C/F/TAF FDC in HIV-1 infected adults with ESRD on chronic HD at Week 96
- To evaluate the proportion of subjects receiving E/C/F/TAF FDC achieving virologic response (HIV-1 RNA < 50 copies/mL, as defined by the FDA snapshot analysis) at Weeks 24, 48, and 96
- To evaluate plasma pharmacokinetics (PK) of EVG, COBI, FTC, TAF, and tenofovir (TFV) in HIV-1 infected patients with ESRD on chronic HD
- To evaluate the safety and tolerability of bictegravir/emtricitabine/tenofovir alafenamide (B/F/TAF) FDC in HIV-1 infected adults with ESRD on chronic HD in the open-label extension phase

1.2. Study Design

Design Configuration and Subject Population

GS-US-292-1825 is an open-label, multicenter, single-arm study to assess the safety, tolerability, PK, and efficacy of the E/C/F/TAF FDC dosed once daily in HIV-infected adult subjects with ESRD on chronic HD.

All subjects will switch from their current antiretroviral (ARV) regimen to E/C/F/TAF on Day 1. The treatment duration for E/C/F/TAF will be at least 96 weeks.

After Week 96, subjects in the US will continue to take their study drug and attend visits every 12 weeks until the End of E/C/F/TAF visit. At Week 96 or the End of E/C/F/TAF Visit, subjects will discontinue E/C/F/TAF FDC and be given the option to receive open-label (OL) B/F/TAF FDC. All subjects participating in the OL extension of B/F/TAF FDC will return for study visits at B/F/TAF Week 4 OL, Week 12 OL, and every 12 weeks thereafter for at least 48 weeks.

Subjects who do not wish to participate in the B/F/TAF OL extension phase will discontinue study drug at Week 96.

Approximately 50 subjects with ESRD on chronic HD will be enrolled.

Treatment Groups

All enrolled subjects will receive the following treatment:

- FDC of elvitegravir 150 mg/cobicistat 150 mg/emtricitabine 200 mg/tenofovir alafenamide 10 mg administered orally, once daily with food until the next hemodialysis. On the day of hemodialysis, study drug should be administered after completion of hemodialysis.

Subjects who enroll into the B/F/TAF OL extension phase will receive the following treatment:

- FDC of bictegravir 50 mg/emtricitabine 200 mg/tenofovir alafenamide 25 mg administered orally, once daily without regard to food until the next hemodialysis. On the day of hemodialysis, study drug should be administered after completion of hemodialysis.

Key Eligibility Criteria

HIV-infected adults who meet the following criteria:

- No documented history of HIV-1 resistance to EVG, FTC, lamivudine (3TC), or TDF
- Currently receiving a stable ARV regimen for ≥ 6 consecutive months prior to screening
- Plasma HIV-1 RNA < 50 copies/mL for at least 6 months preceding the screening visit
- CD4 cell count of ≥ 200 cells/ μ L
- ESRD with eGFR < 15 mL/min by Cockcroft-Gault (CG)
- On chronic HD for ≥ 6 months prior to screening
- Hepatitis C virus (HCV) infection allowed
- Hepatitis B virus (HBV) infection not allowed

Study Periods / Phases

The study will consist of a 30-day screening period (within 30 days before Day 1 visit), followed by a 96-week E/C/F/TAF treatment period.

After Week 96, all subjects participating in the B/F/TAF OL extension phase will receive B/F/TAF FDC for at least 48 weeks.

End of the study will occur when the last subject enrolled in the study has completed their last observation (or visit).

After a subject has completed/terminated their participation in the study, long-term care of the subject will remain the responsibility of their primary treating physician.

Schedule of Assessments (E/C/F/TAF Phase)

Following Screening, eligible subjects will be required to return for study visits at Day 1 and Weeks 2, 4, 8, 12, 24, 36, 48, 60, 72, 84, and 96. After the Week 96 visit, subjects who are not planning to participate in the B/F/TAF OL extension phase will stop study drug and complete a 30-day Follow-up visit to complete their participation in the study. Subjects who plan to participate in the B/F/TAF OL extension phase will continue to take E/C/F/TAF and attend visits every 12 weeks until the End of E/C/F/TAF visit.

For all subjects, HBV and HCV serologies will be analyzed at Screening. Adverse events (AEs), concomitant medications, complete or symptom-directed physical examinations, laboratory analyses (hematology and chemistry), HIV-1 RNA, and CD4 cell count will be assessed at Screening, Day 1, and all subsequent study visits. eGFR will be assessed at Screening, Day 1, and all subsequent study visits except the 30-day Follow-up visit. Fasting lipids and glucose will be assessed at Day 1 and every 24 weeks thereafter until Week 96 or End of E/C/F/TAF visit.

Predose whole blood draw for plasma and peripheral blood mononuclear cell (PBMC) samples will be collected from all subjects at Week 4 or Week 12, which must be the day of hemodialysis.

CC1

Schedule of Assessments (B/F/TAF OL Extension Phase)

All subjects participating in the B/F/TAF OL extension phase will return for study visits at B/F/TAF Week 4 OL, Week 12 OL, and every 12 weeks thereafter for at least 48 weeks.

Adverse events, concomitant medications, complete or symptom-directed physical examinations, laboratory analyses (hematology and chemistry), HIV-1 RNA, and CD4 cell count will be assessed at each visit. eGFR will be assessed at each visit except the 30-day Follow-up visit. Fasting lipids and glucose will be assessed every 24 weeks.

Site and Stratum Enrollment Limits

Approximately 25 study sites in North America and Europe will participate. There is no enrollment limit for individual sites.

